7.3 Assignment of treatment

- It is a non-comparative, open-label study. All patients will receive the same treatment.

7.4 Outcome variables

7.4.1 Primary outcome variables

- Incidence of unexpected PI-related AEs.
- Incidence of IP-related photophobia.

7.4.2 Secondary outcome variables

- Changes in pupillary diameter.
- Incidence of expected PI-related AEs.
- Changes in visual acuity.

7.4.3 Exploratory variables

- Changes in the AVMC.
- Intraocular pressure (IOP) changes.
- Corneal and conjunctival staining changes with fluorescein and lysmine green.
- Changes in vital signs (heart rate and blood pressure).
- Changes in OCI.

7.4.4 Definition of variables, methods and scales for their measurement

Board 1. Operational definition of variables

Variable	Conceptual Definition	Operational Definition	Measurement Type	Reference value	Statistical test
Incidence of unexpected-IP-related AEs	Any adverse medical event that occurs in the clinical research subject to whom the PI was administered that has a certain causal relationship with the PI and is not expected. [36]	All AEs (according to the protocol) in which the PI suspects a causal relationship with the PI will be reported.	
 • Discrete quantitative • Nominal qualitative 	< 10%	
 • U for Mann Whitney • Pearson X² or Fisher Exact*
Photophobia incidence	Expected-PI-related AE	Present / Absent	
 • Discrete quantitative • Nominal qualitative 	< 15%	
 • U for Mann Whitney • Pearson X² or Fisher Exact*
Pupillary diameter	The natural pupil of the human eye is usually approximately circular, for a given subject, the pattern of aberrations, diffraction, depth of field and retinal illumination depends on the pupillary diameter, which in turn	The pupillary diameter results from the balance between the pupil sphincter muscle and the radial fibers of the iris that have only autonomic innervation. [37] It will be evaluated through the OPD scan.	Continuous quantitative	2 – 6 mm	Kolmogorov-Smirnov or Mann Whitney U*

Variable	Conceptual Definition	Operational Definition	Measurement Type	Reference value	Statistical test
	varies depending on the ambient lighting.				
Incidence of AD	Any adverse medical event that occurs in the clinical research subject to whom the PI was administered. [36]	All AEs (according to the protocol) will be reported and not just those where the PI suspects a causal relationship with the PI	• Discrete quantitative • Nominal qualitative	• Incidence • Seriousness (severity) • Causality	• U for Mann Whitney • Pearson X ² or Fisher Exact*
Changes in the AVMC	Clinical assessment of near visual acuity allows visual ability to distinguish letters to be assessed.	It will be evaluated by means of the ETDRS booklet for near vision (annex16.1 ETDRS Primer for Near Vision), using the font size in logMAR.	Continuous quantitative	0.1 or better	Kolmogorov-Smirnov or Mann Whitney U*
Changes in the AVMC	Visual spatial acuity is the ability to distinguish separate elements of an object and identify them. It is quantified as the minimum angle of separation (located at the nodal point of the eye) between two objects that allows them to be perceived as separate objects.	Snellen Primer on logMAR	Continuous quantitative	0.2 or better	Kolmogorov-Smirnov or Mann Whitney U*
Intraocular Pressure	Tonometry is the objective measurement of IOP, based on the force required to flatten the cornea or the degree of corneal indentation produced by a fixed force.	By means of Goldmann tonometry based on the Imberk-Fick principle.	Discrete quantitative	10 – 21 mmHg	Kolmogorov-Smirnov or Mann Whitney U*
Changes in ocular surface staining	Detection of epithelial defects in the cornea and conjunctiva.	Direct observation with a slit lamp will be graded according to SICCA (see annex 16.2 SICCA Eye Staining Rating (modified from Whitcher et al, 2010) [38].	Discrete quantitative	0 to 12	Kolmogorov-Smirnov or Mann Whitney U*
Changes in vital signs	It includes the measurement of HR, SBP and DBP. They are clinical parameters that reflect the physiological state of the organism.	HR, SBP and DBP will be measured with an electronic blood pressure monitor or manually.	Discrete quantitative	HR: 60 – 100 bpm SBP: 120 – 139 mmHg DBT: 80 – 89 mmHg	Kolmogorov-Smirnov or Mann Whitney U*
OCI Score	The OCI is a questionnaire designed to measure irritation of the ocular surface, it assesses symptoms focused on the comfort associated with ocular surface alterations.	The evaluator will apply the questionnaire to the subject and will allow the subject to answer it calmly without any pressure and/or	Discrete quantitative	0 – 100	Kolmogorov-Smirnov or Mann Whitney U*

Variable	Conceptual Definition	Operational Definition	Measurement Type	Reference value	Statistical test
	Elevated values indicate more severe symptoms.	coercion (see annex 16.3 Ocular Comfort Index (OCI))			

Abbreviations: AVMC, best corrected visual acuity; CVA, near best corrected visual acuity; AE, adverse event; HR, heart rate; OCI, ocular comfort index; PI, principal investigator; bpm, beats per minute; DBP, diastolic blood pressure; SBP, systolic blood pressure; IOP, intraocular pressure; rpm, breaths per minute; TF, fluorescein staining; IP; principal investigator; χ^2 , Chi-square.

*When applicable.

7.4.5 Description of the variables, methods and scales for their measurement

For clinical purposes, ophthalmological evaluations will be carried out in both eyes, and their record will be recorded in the clinical file. However, to obtain results and comply with the assumption of independence within the variables, only examinations and qualifications of the right eye will be recorded in the eCRF when appropriate. Next, the description of the variables is made, which are not in order of execution.

7.4.5.1 Intraocular pressure

Tonometry is the objective measurement of IOP, based primarily on the force required to flatten the cornea or the degree of corneal indentation produced by a fixed force. Goldman tonometry is based on the Imbert-Fick principle. [39]

The tonometry will be performed, after instillation of the topical anesthetic, with fluorescein and the use of the cobalt blue filter (after the evaluation of the surface staining). 2 samples will be taken, and the average will be calculated, which will be recorded in the clinical file. The average will be recorded in the eCRF.

Management as AE: IOP peaks ≥ 24 mmHg should be reported as AEs.

7.4.5.2 Heart rate

Heart rate is the number of times the heart ventricles contract per unit of time, usually per minute. The heart rate measurement will be done by direct auscultation in the chest with a stethoscope. In the case of measuring, it in women, it may be allowed to measure it on the pulse of the wrist. However, the method chosen for the patient will be the same to be used on all visits. [40]

For the measurement of the heart rate, it will be necessary for the patient to be calm and in a state of rest. You will be asked to rest for at least 20 minutes upon arrival at the clinic, before your measurement, and when you are due to be assessed after the application of the medication, you should also have a 20-minute rest period.

For protocol issues, we refer to rest or rest as the state where the patient does not have agitation because of unnecessary physical effort. The patient should be seated for most of the rest of the period, being able to get up to walk to go to the bathroom.

Management as AE: Patients with heart rates greater than 100 bpm or less than 60 bpm.

7.4.5.3 Systemic Blood Pressure

It is the force exerted by blood circulation on the walls of the arteries. Blood pressure is assessed with two measurements: systolic (measured when the heart beats and is when the pressure is at the highest) and diastolic (measured between beats, when the pressure is at the lowest point). When it is reported, the systolic is written first and then the diastolic. [41]

A calibrated aerobic or mercury sphygmomanometer and stethoscope will be used to measure it. The left arm should be used for the measurement, and it should be done at rest.

Management as AE: Patients with systolic blood pressure of 140 mmHg or higher and diastolic blood pressure of 90 mmHg or higher.

7.4.5.4 Photophobia

Photophobia is a sensory disturbance caused by light, it is considered a common symptom seen in neurological and ophthalmological conditions. According to Albilali (2018) it can be induced by glare; It was described as "uncomfortable vision, based on the diffusion of light through the ocular means or on a transient or permanent lack of adaptation." It involves an uncomfortable sensation of excessive brightness without pain, and occurs mainly with eye diseases, such as toxic, amblyopia, albinism, rod monochromatism, and corneal, lenticular, and vitreous opacities. In this study, it may occur secondary to pharmacological mydriasis generated using atropine sulfate. [42]

Photophobia will be assessed within the adverse event interrogation according to the 8. Evaluation and management of adverse events, without questioning in a directed way within visit 1, final visit and security call. It will be reported as present or absent.

7.4.5.5 Pupillary diameter

It is the hole in the middle of the iris through which light penetrates the eyeball. Its diameter results from the balance between the pupil sphincter muscle and the radial fibers of the iris (pupil dilator). Normal values are 2-6 mm. [37]

In higher concentrations this product is mydriatic, however, due to the nature of the research and the physicochemical characteristics this reaction is not expected to occur, we will consider as significant the change that is generated in the pupil of the research subjects > 2 mm (pharmacological mydriasis), whether this change in photopic or mesopic vision. The method to perform the measurement will be using the following tool: OPD-Scan III (NIDEK CO., LTD, Tokyo, Japan). It is requested that the tool used be the same for all patients of the research center and for all their visits. It is necessary that the measurement is always done in the same office, with the same artificial light conditions and that the patient has at least 5 minutes inside the place before the measurement.

If there is a change greater than 2 mm between baseline and any of the other measurements, the product will be considered to have produced pharmacological mydriasis. This change will also be considered an adverse event.

7.4.5.6 Best-corrected visual acuity

Visual acuity (VA) is a test of visual function. Visual spatial acuity is the ability to distinguish separate elements of an object and identify them. It is quantified as the minimum angle of separation (located at the nodal point of the eye) between two objects that allow them to be perceived as separate objects.

Snellen's notation is described as the distance at which the test is performed, divided by the distance at which the letter is vertically equivalent to 5 arc minutes. Thus, at 6 meters a letter 6/6 (20/20) is equivalent to 5 minutes of arc, a letter 6/12 (20/40) is equivalent to 10 minutes, and a letter 6/60 (20/200) is equivalent to 50 minutes. The Snellen fraction can also be expressed as a decimal place (i.e., 20/20 = 1 and 20/40 = 0.5). [34]

VA will be evaluated at baseline, without refractive correction with the Snellen chart. It will be in a place with adequate lighting (natural or artificial) and at 3m from the subject to be evaluated. Visual acuity of the right eye will be taken initially, asking the subject to hold both eyes open and using an occlude to cover the contralateral eye; the subject will read aloud the lines that the evaluator points out, the line of smaller letters that he can see will be noted by the evaluator in fraction as the AV of OD in the clinical record and the eCRF, then the same evaluation will be performed in the left eye and its record only in the clinical file.

Next, the subject's best refractive correction (obtained by autokeratometer and subjective tests) will be evaluated and the examination will be repeated using the refraction obtained. This result will be reported as best-corrected visual acuity, both data will be reported for statistical purposes in logarithmic figures (LogMAR) and in eCRF.

A fraction conversion table is attached to LogMAR. (see annex 16.4 Fraction to LogMAR conversion table.)

Management as AE: A decrease in 2 or more lines of sight in BCVA compared to that obtained at baseline will be considered an adverse event.

7.4.5.7 Best Corrected Visual Acuity Near

Visual Acuity (VA) is the characteristic of vision that determines the ability to detect, discriminate, and recognize objects on a background at a close distance. It assesses macular function and provides information on the accuracy of retinal focus, as well as the integrity of the neurological elements of the eye and the interpretive ability of the brain.

Near visual acuity (NVA) will be assessed, without refractive correction with the ETDRS chart. It will be in a place with adequate lighting (natural or artificial) and at 35 to 40 cm from the subject to be

evaluated. Visual acuity of the right eye will be taken initially, asking the subject to hold both eyes open and using an occluder to cover the contralateral eye; the subject will read aloud the lines that the evaluator points out, the line of smaller letters that he can see will be noted by the evaluator in fraction as the AVC of OD in the clinical record and the eCRF, then the same evaluation will be performed on the left eye and its record only in the clinical file.

Next, the subject's best refractive correction (obtained by autokeratometer and subjective tests) will be evaluated and the examination will be repeated using the refraction obtained. This result will be reported as best corrected near visual acuity (CVA), both data will be reported for statistical purposes in logarithmic figures (LogMAR) and in the eCRF. It is necessary that the measurement is always done in the same office, with the same light conditions.

A fraction conversion table is attached to LogMAR. (see annex 16.4 Fraction to LogMAR conversion table.)

Management as AE: A decrease in 2 or more lines of sight in the CVVA compared to that obtained at baseline will be considered an adverse event

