
Elimination criteria:
 
 – Withdrawal of the letter from the FCI. – Presentation of a serious adverse event related or not to the investigational product, which at the discretion of the PI and/or sponsor could affect the patient's ability to continue with the study procedures safely. – Non-tolerability or hypersensitivity to any of the compounds used during the tests (fluorescein, lysmine green, tetracaine). – No tolerability or hypersensitivity to the investigational drug. – Adherence < 90% determined by the subject's diary 	

Research Product (PI):
 
 - PRO-201 . Atropine Sulfate 0.01%. Zapopan, Jalisco, Mexico. Ophthalmic solution Laboratorios Sophia, S.A. de C.V - Dosage: 1 drop once a day (QD) in the evening, in both eyes (AO). - Route of administration: Ophthalmic 	

Duration of treatment: 14 days
	
Duration of the subject in the study: 21 days

Evaluation criteria:
 
Primary outcome variables
 
 – Incidence of unexpected PI-related AEs (Time of Assessment [TE]: days 7, 16 and 21) – Incidence of IP-related photophobia. (TE: 7th, 16th and 21st) 
Secondary outcome variables:
 
 – Changes in pupillary diameter (ET: day 7 and 16). – Incidence of expected PI-related AEs (TE: days 7, 16, and 21). – Changes in visual acuity (TE: day 7 and 16). 
Exploratory variables:
 
 – Changes in the AVMC (TE: day 7 and 16). – Intraocular pressure (IOP) changes (ET: day 7 and 16). – Changes in corneal and conjunctival staining with fluorescein and lysmine green (ET: day 7 and 16). – Changes in vital signs (heart rate and blood pressure) (ET: day 7 and 16). – Changes in the OCI (TE: day 16). 	

Statistical methodology
 
The analysis of the data collected in the study will be carried out using the SPSS version 19.0 statistical package. For continuous and discrete quantitative variables, data will be expressed by
	

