1.3 Subject Timeline

Procedures	VB	V1	VF	SC
	D 1	D 7 ± 1	D 16 ± 1	D21 ± 1
Informed Consent Form (FCI) Signature	X			
Medical history	X			
Eligibility Criteria	X			
Concomitant Drug Evaluation	X	X	X	
Urine pregnancy test	X		X	
Vitals signs	X	X	X	
Best Corrected Visual Acuity (BCVA)	X	X	X	
Best Corrected Near Visual Acuity (BCNVA)	X	X	X	
Pupillary diameter measurement	X	X	X	
Evaluation of fluorescein staining and lysmine green	X	X	X	
PIO	X	X	X	
Comprehensive ophthalmological evaluation	X	X	X	
Adverse Event (AE) Assessment	X	X	X	X
Subject Code Assignment and Research Product (PI)	X			
Eye Comfort Index (ECI)	X		X	
Delivery of the PI and initiation of intervention	X			
Daily subject delivery	X			
Adherence assessment		X	X	
Return / evaluation of the subject's diary			X	
Return of PI			X	

2. Introduction and background

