2.4 Risk-benefit assessment

2.4.1 Known potential risks

Formulations containing atropine sulfate at the same concentrations as PRO-201 are products that are marketed in Asia, as well as in compounding formulations in other countries in the Americas and Europe. The risks of using this product in specific populations are described below, however, the use of this drug in the study will be in a population group without the alterations or characteristics described below. To Concentration at 0.01% The potential risks are: photophobia, mydriasis, difficulty reading, allergic eye reactions (atopic dermatitis, allergic conjunctivitis and other allergic reactions), eye irritation, burning eyes, eye pain, tearing, foreign body sensation, dry eye, hyperemia and/or red eye, blurred vision, eye itching; Systemic adverse events include: headache, drowsiness, dizziness, tachycardia, flushing, restlessness, irritability, dry skin, dry mouth, skin rash and decreased alertness. [8] [6] [18] [19] [20] [21] [22] [23] [24]

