3.1.2.2 Secondary

- To evaluate the safety of PRO-201 ophthalmic solution applied to the ocular surface in healthy volunteers, by evaluating the pupillary diameter by the OPD scan.
- To evaluate the safety of PRO-201 ophthalmic solution applied to the ocular surface in healthy volunteers, using the incidence of expected PI-related AEs.
- To evaluate the tolerability of PRO-201 ophthalmic solution applied to the ocular surface in healthy volunteers, by evaluating the best corrected near visual acuity (CVA) with the ETDRS primer.

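### Near acuity, a secondary tolerability endpoint, is read through a lens and at a distance that the plan does not hold constant, so a loss of near focus may be masked in the corrected value and in the adverse-event rule

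*Combined protocol and SAP*

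**What the plan says.** The secondary tolerability objective (section 3.1.2.2) is to be met "by evaluating the best corrected near visual acuity (CVA) with the ETDRS primer". The timeline in section 1.3 lists "Best Corrected Near Visual Acuity (BCNVA") at baseline, Visit 1 and the Final Visit, and the visit lists in section 7.7 agree.

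Section 7.4.5.7 orders two readings:

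- **Uncorrected.** "Near visual acuity (NVA) will be assessed, without refractive correction with the ETDRS chart".
- **Corrected.** Next, "the subject's best refractive correction (obtained by autokeratometer and subjective tests) will be evaluated and the examination will be repeated using the refraction obtained".

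Of the two results, "both data will be reported for statistical purposes in logarithmic figures (LogMAR) and in the eCRF". The chart is placed "at 35 to 40 cm from the subject". Office and lighting must be the same each time; lens and distance are not mentioned. An adverse event is a loss of two or more lines from baseline on the corrected reading.

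The outcome label in the synopsis is only "Changes in visual acuity (TE: day 7 and 16"). It does not say near or far, corrected or uncorrected, and section 7.4.2 is no more specific. Board 1 (section 7.4.4) gives its near and distance rows the same name, and section 10.3.1 speaks only of near visual acuity.

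Section 2.4.1 lists "photophobia, mydriasis, difficulty reading" among the potential risks at 0.01%.

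**The concern.** The endpoint is there to show whether an antimuscarinic drop impairs near vision. The relevant mechanism is reduced ability to focus at reading distance. A best-corrected reading asks how well the eye sees once the lens has been optimised. If the lens is re-optimised after dosing and may include plus power for near, it can supply the focusing that the drug took away. The recorded change from baseline then understates the effect, and the 2-line rule may not trigger.

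The study has one arm and is open-label, so no control group could show that the test is insensitive. The variable distance is a separate weakness: it moves the recorded acuity with no change in the eye.

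**Working it through.** The plan gives no figure for this endpoint (no SD, no power, no expected change), so there is nothing of its own to reproduce. The inputs are the 35 to 40 cm range and the 2-line rule from section 7.4.5.7, and the step of 0.1 logMAR per line from the conversion table in annex 16.4. The rule is therefore a threshold of 2 × 0.1 = 0.2 logMAR.

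**Lens.** Focusing demand is 1 / distance in metres:

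- at 40 cm, 1/0.40 = 2.50 D
- at 35 cm, 1/0.35 = 2.86 D

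The documents give no accommodation data, so usable focus after dosing is an assumption. For 0.5 to 2.0 D of usable focus and no other refractive error, the unmet demand is:

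| Usable focus | Deficit at 40 cm | Deficit at 35 cm |
|---|---|---|
| 0.5 D | 2.00 D | 2.36 D |
| 1.0 D | 1.50 D | 1.86 D |
| 1.5 D | 1.00 D | 1.36 D |
| 2.0 D | 0.50 D | 0.86 D |

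A near addition equal to the deficit removes it from the corrected reading: change near zero and no adverse event. A smaller addition removes part of it. A distance refraction removes none of it, because an eye corrected for distance must still meet the full 2.50 to 2.86 D itself. If reduced accommodation also brought out a hyperopic shift, a repeated distance refraction would absorb that shift but not the near demand.

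**Distance.** A line of fixed letter size changes its visual angle with distance:

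- shift = log10(40/35) = 0.058 logMAR
- in lines, 0.058 / 0.1 = 0.58
- share of the adverse-event threshold, 0.058 / 0.2 = 29%

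If baseline is read at 40 cm and follow-up at 35 cm, a true loss of 0.20 appears as 0.20 − 0.058 = 0.142, below the threshold. In the reverse order it appears as 0.20 + 0.058 = 0.258.

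To set this against what the trial could detect, assume an SD of change of 0.05 to 0.15 logMAR. With 24 subjects, two-sided alpha 0.05, 80% power and a normal approximation, the detectable mean change is (1.960 + 0.842) × SD / √24, which is 0.029 to 0.086 logMAR. A shift of 0.058 shared by all subjects would lie within that range. A shift that varies at random between subjects would add noise instead.

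**Uncorrected reading.** Section 5.1.1 limits corrected acuity but not refractive error, so myopic subjects can enter. An uncorrected eye of about −2.5 D is focused at 1/2.5 = 0.40 m without accommodating. Its uncorrected near reading may hardly change when focusing is lost.

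**The case against.** The strongest reply is that section 7.4.5.7 already takes an uncorrected near reading first and keeps it for statistics. A reader might infer that the drug effect is corrected away before it is measured, or that the endpoint is blind to it. The documents do not support that: a lens applied second cannot erase a reading taken first. The safeguard is nevertheless incomplete. The adverse-event rule does not use that reading, the objective names the corrected one, and the uncorrected value is insensitive in some myopic eyes.

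A reader might also take it as stated that the refraction is redone at every visit. It is not. Repetition is the natural reading of a procedure scheduled three times, but no separate refraction appears in the visit lists, and carrying the baseline lens forward is not excluded.

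Nor does the plan mention a near addition. Section 7.4.5.6 describes the distance refraction in the same terms, so an ordinary distance lens is at least as natural a reading, and it would leave most of the loss visible. This stands, and it makes the masking conditional.

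Finally, reading difficulty and blurred vision are listed as adverse events that can occur (section 7.4.5.9), and the incidence of expected related events is itself a secondary outcome. That is another route to detection, but it relies on adverse-event reporting and does not replace a measured endpoint.

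**Conclusion.** The concern holds as a gap in specification. The corrected near reading, which carries both the objective and the 2-line rule, has no fixed lens, no restriction to a distance refraction and no single test distance, and the plan does not clearly state which of the two recorded near values is analysed.

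The size of any masking depends on two things the plan leaves open: whether the refraction is repeated after baseline, and whether it includes plus power for near. If both apply, a deficit of 0.5 to 2.0 D at 40 cm (under the assumed usable focus) could be partly or wholly hidden. With a distance-only refraction, most of it would show.

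The distance effect does not depend on those conditions: up to 0.058 logMAR, or 0.58 line. It can go either way, so it should not be read as a bias towards calling the product tolerable. This is a secondary endpoint; the two primary outcomes and the sample size are unaffected.

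**What to change.** In section 7.4.5.7, specify that near acuity at baseline, Visit 1 and the Final Visit is read through the distance refraction obtained at baseline, with no near addition, at one fixed distance (for example 40 cm). Name this distance-corrected reading as the analysed secondary endpoint and apply the existing 2-line threshold to it. Report uncorrected near acuity as supportive. Align the wording in the synopsis, sections 3.1.2.2 and 7.4.2, Board 1, section 10.3.1 and the timelines. Distance acuity can keep its own refraction.

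The cost is protocol wording and a site instruction; visits, threshold and sample size do not change. There are two downsides. A true refractive change would also appear as near-acuity loss, which is acceptable for a tolerability measure. The endpoint label also changes from best-corrected to distance-corrected near acuity.
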